4.7.2. Adverse Events

The MedDRA PT derived from the verbatim term will be used when reporting AEs by MedDRA terms. The MedDRA Lower Level Term will be used in the treatment-emergent computation. Toxicity grades will be assigned by the investigator using NCI-CTCAE version 5.0.

Pre-existing conditions are defined as AEs that either are ongoing at informed consent or end on or after informed consent. Pre-existing conditions will be included in the listing of AE so that the history of AEs can be traced.

Treatment-emergent adverse events are events that first occur or worsen in CTCAE grade after the first dose of study treatment, and up to 30-day short-term follow-up visit. Treatmentemergent adverse events will be summarized by SOC and by decreasing frequency of PT within SOC.

CONFIDENTIAL

Adverse event analyses will include summaries of the following:

- overview of AEs
- TEAEs, including toxicity grade (any grade and grade ≥3) and possible relationship to study drug
- serious AEs, including possible relationship to study drug
- AEs leading to dose adjustments/omissions
- discontinuations from study treatment due to AEs or death, and
- time to onset for selected TEAEs.

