8.3.4. Adverse Events of Special Interest

Adverse events of special interest for abemaciclib include

	neutropenia
	infections
	diarrhea
	hepatic events, including increases in AST/ALT
	VTEs, and
	ILD/pneumonitis.
No AE	es need to be adjudicated.

Section 6.8.1 describes supportive care measures for each abemaciclib AESI. Sections 6.5.1.1 and 6.5.1.2 present the dose-modification guidelines for abemaciclib AESIs.

Contact the Sponsor CRP/CRS if questions arise concerning AESIs.

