4.7.1. Extent of Exposure

Drug exposure, dose intensity, and drug adjustment (dose omissions, increases, reductions, interruptions, and delays) for abemaciclib/placebo and fulvestrant will be summarized for all treated patients per treatment arm. Drug exposure will include summaries of cycles received per patient, duration on therapy, and cumulative dose. Dose intensity will be calculated as the actual cumulative amount of drug taken divided by the duration of treatment. Relative dose intensity will be calculated as the actual amount of drug taken divided by the amount of drug prescribed times 100% (expressed as a percentage).

For abemaciclib/placebo, extent of exposure will be measured by pill counts and summarized cumulatively. The summary will include total dosage taken, dose intensity, and relative dose intensity. The assigned cumulative dose for each patient during each cycle is 150 mg per dose \times 2 doses per day \times 28 days = 8400 mg. The assigned cumulative dose while on study is 150 mg per dose \times 2 doses per day \times number of days on treatment.

For fulvestrant, extent of exposure will be measured using the fulvestrant administration eCRF and summarized by cycle and cumulatively. The summary will include total dosage administered, dose intensity, and relative dose intensity. The assigned cumulative dose for each patient during each cycle is 1000 mg for Cycle 1 and 500 mg for Cycle 2 and beyond. The assigned cumulative dose while on study is 500 mg + 500 mg × number of cycles started.

Dose adjustments and omissions, along with the reason for adjustment or omission, will be summarized for abemaciclib/placebo and fulvestrant.

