Abbreviations: HR = hazard ratio; PFS = progression-free survival; NA = not applicable.

5. Sample Size Determination

The study will randomize approximately 350 participants in 1:1 randomization ratio, with approximately 175 participants per treatment arm.

A 2-look group-sequential design of the primary endpoint of investigator-assessed PFS will be used to accommodate an event-driven plan for an interim PFS and final PFS analyses. The interim efficacy analysis will be performed after approximately 176 PFS events in total have occurred (ie, approximately 70% of the planned PFS events).

The final PFS analysis will be performed after approximately 251 PFS events in total have occurred (that is, an approximately 30% censoring rate). Assuming a hazard ratio of 0.70, this sample size yields approximately 80% statistical power to detect superiority for the abemaciclib plus fulvestrant arm versus the placebo plus fulvestrant arm.

This will be conducted with a one-sided log-rank test and a cumulative Type I error of 0.025.

6. Supporting Documentation

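### SAP 4.7.2 tabulates TEAEs as crude frequencies over a window whose length depends on progression, with no exposure-adjusted or fixed-time summary named

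*SAP*

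**What the plan says.** SAP 4.7.2 defines TEAEs as events that "first occur or worsen in CTCAE grade after the first dose of study treatment, and up to 30-day short-term follow-up visit". They are summarised by system organ class and by preferred term in decreasing frequency. The section also lists summaries by grade and relationship, serious AEs, AEs leading to dose changes, discontinuations due to AEs or death, and onset time for some TEAEs to be selected. It gives no method, term list or censoring rule for the onset-time item.

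Exposure is handled separately, in SAP 4.7.1: "Drug exposure will include summaries of cycles received per patient, duration on therapy, and cumulative dose". Nothing in the readable text of SAP 4.7 combines exposure with the AE counts.

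Under the estimand in SAP 1.1, treatment ends at progression, unacceptable toxicity or another protocol-defined reason. SAP Section 5 sets the design: "approximately 350 participants in 1:1 randomization ratio", with the final PFS analysis at about 251 events. "Assuming a hazard ratio of 0.70, this sample size yields approximately 80% statistical power".

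Protocol 8.3.4 begins "Adverse events of special interest for abemaciclib include" and lists six: neutropenia, infections, diarrhea, hepatic events, venous thromboembolism and ILD/pneumonitis. SAP 4.7.2 does not name them. The list of safety summaries in Protocol 9.3.4 cannot be read in this extract, so this point is confined to the SAP.

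**The concern.** If abemaciclib delays progression as the design supposes, its patients stay in the TEAE window longer. An event that occurs at the same rate per month in both arms is then seen in more abemaciclib patients. A reader of the crude table cannot tell how much of a difference is toxicity and how much is observation time.

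Characterising the safety of abemaciclib with fulvestrant is a secondary objective. The ambiguity matters most for less common events that can occur at any time on treatment, such as venous thromboembolism, infection and ILD/pneumonitis. The size and direction of the distortion depend on the efficacy result and on why patients stop, so the remedy is better fixed before unblinding than chosen afterwards.

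**Working it through.** **1. The plan's own figure.** The documents state no AE excess or exposure ratio, so the design is checked first.
- Inputs (SAP 4.9.3 and Section 5): 176 and 251 events, HR 0.70, O'Brien-Fleming type spending, and a "one-sided log-rank test and a cumulative Type I error of 0.025".
- Information fraction: 176/251 = 0.701.
- Interim: alpha spent = 2[1 − Φ(2.2414/√0.701)] = 0.0074, so z = 2.436 and the HR boundary is exp(−2 × 2.436/√176) = 0.693. Power = 1 − Φ(2.436 − 0.3567 × √176/2) = 0.472.
- Final: p boundary 0.0227, HR boundary 0.777, cumulative power 0.801.

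SAP Table 6 gives 0.007, 0.69 and 0.472 at the interim, and 0.023, 0.78 and 0.801 at the final. These agree.

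**2. Assumptions for the AE calculation.** HR 0.70, 350 patients and 251 events come from the plan. The following are not in the documents:
- control median PFS of 3-8 months, with exponential PFS
- uniform accrual over 12-24 months
- AE rate r of 5-30 per 100 patient-years, constant and equal in both arms
- treatment ending at progression, followed by a 30-day tail

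**3. Every patient followed to progression.** Incidence = 1 − exp(−r × 30/365) × m/(m + r), with m = ln 2/median (in years) for control and 0.70m for abemaciclib. With a 5-month median, m = 1.664 per year.

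| Rate per 100 patient-years | Control | Abemaciclib | Ratio |
|---|---|---|---|
| 5 | 3.3% | 4.5% | 1.36 |
| 30 | 17.3% | 22.4% | 1.29 |

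Over medians of 3-8 months the ratio runs from 1.27 to 1.37. The ratio of mean windows is 1.35-1.39. Without the 30-day tail it would be 1/0.70 = 1.43.

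**4. At the planned PFS analysis.** 251/350 = 71.7% have an event, so 28.3% are censored. The cut-off T is the time at which the average event probability over the two arms reaches 251/350. Each patient's window is the smaller of PFS + 1 month and T − entry time, and incidence = 1 − E[exp(−r × window)].

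For a 5-month median and 18-month accrual, T = 21.5 months and the mean windows are 6.33 and 7.47 months (ratio 1.18).

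| Rate per 100 patient-years | Control | Abemaciclib | Ratio | Difference in patients per 175 |
|---|---|---|---|---|
| 5 | 2.6% | 3.0% | 1.18 | 0.8 |
| 30 | 14.2% | 16.5% | 1.16 | 4.0 |

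Over the whole assumed range the window ratio is 1.16-1.22 and the ratio of patients with an event is 1.15-1.22. If all censoring were instead dropout that ends the window, the window ratio would be 1.22-1.26.

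**5. Common and early-onset events.** At the 251-event cut the ratio is 1.09-1.12 for an AE with 50% control incidence and 1.03-1.06 at 80%. For an uncommon AE confined to the first 2-3 months on treatment it is about 1.01-1.03 (control medians of 4-6 months).

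**6. Stopping for reasons other than progression.** Add monthly hazards a (abemaciclib) and b (control) of leaving treatment. With full follow-up, the window ratio = [1/(0.7λ + a) + 1]/[1/(λ + b) + 1]. With a 5-month median, λ = 0.1386, and b = 0.01:
- a = 0.02: 1.23
- a = 0.03: 1.15
- a = 0.05: (6.80 + 1)/(6.73 + 1) = 1.01
- a = 0.07: (5.99 + 1)/(6.73 + 1) = 0.90

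These hazards are illustrative. They show that the excess can vanish or reverse.

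**The case against.** The strongest case against is that little rides on this. AE outputs are descriptive, no between-arm test is planned, and only PFS and OS are error controlled. Exposure is tabulated by arm, so readers will see unequal durations. In absolute terms the artefact is small: under one patient per arm for an event at 5 per 100 patient-years in the worked case. Protocol 2.3.1 places the highest toxicity risk in the early cycles, where the effect nearly disappears. Protocol 8.3 also keeps SAEs caused by the cancer out of the reports unless possibly related to treatment, which removes part of the background. All of this stands. It limits the size of the point but does not supply a time-at-risk summary, and a separate exposure table does not let a reader recover one for a given event.

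Three stronger readings are tempting and are not supported:
- **A general excess of 30-35%.** That needs near-complete follow-up to progression, a constant hazard and an uncommon event. The plan's primary analysis has about 30% censoring. Protocol 9.3.1 makes later updates possible but optional.
- **That nothing time-based is planned, or that the onset-time summary covers only patients with the event.** SAP 4.7.2 lists that summary without a method, so a Kaplan-Meier or cumulative-incidence display is not excluded.
- **That the bias always runs against abemaciclib.** Earlier stopping on that arm can cancel or reverse it. Under Protocol 6.5.1, however, a patient who stops only the blinded drug may continue fulvestrant, and Protocol 1.3 times the follow-up visit from the decision to stop all study treatment. Only patients who leave all treatment shorten the window.

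**Conclusion.** The point holds as a cheap improvement to the safety analysis. It does not affect the primary inference. SAP 4.7.2 commits to unadjusted TEAE frequencies over a window that depends on progression, and its readable text names no exposure-adjusted or fixed-time summary.

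Under HR 0.70, equal constant AE hazards and stopping at progression, an uncommon AE would appear about 15-22% more often on abemaciclib at 251 events. That rises towards 27-37% with full follow-up, with no drug effect. The direction and mechanism follow from the plan. The figures rest on an assumed median PFS, accrual period and AE rates, and they overstate the effect for common or early-onset events and where non-progression discontinuation is higher on abemaciclib.

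**What to change.** Keep the crude tables. Add to SAP 4.7.2 one by-arm table of exposure-adjusted incidence: patients with a first event divided by total time at risk (first dose to first event or end of the TEAE window), per 100 patient-years, with the between-arm difference and 95% CI. Cover any TEAE, Grade ≥3 TEAEs, serious AEs, and each of the six AEs of special interest in Protocol 8.3.4 as a grouped term. For those six, also give cumulative incidence at a fixed time such as 6 months.

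The cost is one extra descriptive table from dates already collected, with no change to design, alpha or conduct. The drawback is that a patient-year rate assumes a roughly constant hazard, which early-onset events such as diarrhea may violate. The fixed-time cumulative incidence covers that case.

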4.7.3. Additional Safety Assessments

Deaths

- Deaths and their primary cause
- Adverse events leading to death

Laboratory Abnormalities

The severity of laboratory results will be classified according to NCI-CTCAE. The laboratory toxicity by worst NCI-CTCAE grade and shifts in toxicity grading from baseline to the worst post-baseline grade will be summarized. Abnormal laboratory parameters will be listed.

Shift to low/high tables will include the number and percentage of patients within each baseline category (baseline value is low, normal, high, or missing) versus each postbaseline category (worst value is low, normal, high, or missing) by treatment arm.

The analyses of AEs, deaths, and laboratory abnormalities will be conducted in the safety population.

Electrocardiograms

Electrocardiogram will be summarized by visit and by treatment arm. A summary of change from baseline (by visit) and the corresponding AEs will also be provided.

Vital Signs

All vital signs (eg, temperature, blood pressure, pulse rate, height, weight, heart rate) will be summarized by visit and by treatment arm. Treatment emergent abnormal changes in vital signs will also be summarized by treatment arm.

4.8. Other Analyses

4.8.1. Demographics

Patient demographics will be summarized. Patient demographics will include the following:

- race
- ethnicity
- geography
- age
- height

- weight
- body mass index
- baseline ECOG performance status

4.8.2. Baseline Disease Characteristics

Disease characteristics will be summarized. Disease characteristics will include the following:

- initial pathological diagnosis
- study entry pathological diagnosis
- disease stage (Stage IIA, Stage IIB, etc.) at initial diagnosis and study entry
- histopathological diagnosis grade (G1, G2, etc.) at initial diagnosis and study entry
- site of disease (liver, lung, etc.)
- measurable disease at baseline (yes versus no)
- presence of visceral metastases (yes versus no)
- number of organs involved (1, 2, or 3+)
- estrogen receptor status, and
- progesterone receptor status

Number of organs involved will be derived from the "Target Tumor: RECIST 1.1" and "Non Target Tumor: RECIST 1.1" case report forms at baseline. All patients with at least one lesion on the target lesion form will be counted as having measurable disease. The number of organs involved will be derived from the location codes of the target and nontarget lesions.

4.8.3. Medical History

Historical conditions and preexisting conditions (using MedDRA PTs) will be summarized by treatment arm.

4.8.4. **Prior Therapy**

Prior radiotherapy, surgery, and systemic therapy will be summarized by treatment arm. Prior radiotherapy and surgery will be categorized by reason for regimen. Prior systemic therapies will be categorized by type of regimen (endocrine therapy, chemotherapy, etc.) and reason for regimen (neoadjuvant, adjuvant, locally advanced, or metastatic). Frequency of each specific therapy will be tabulated within each type of therapy and per reason for regimen.

Most recent CDK4 & 6 inhibitor-based regimen and the duration of that therapy will be summarized within each of the following subgroups:

- Patients whose most recent CDK4 & 6 inhibitor-based regimen was an adjuvant therapy
- Patients whose most recent CDK4 & 6 inhibitor-based regimen was for locally advanced or metastatic disease.

This summary will include median duration of treatment (date of end of therapy – date of start of therapy + 1), median time to progression (date of progression – date of first dose + 1), and frequency of each specific therapy. If only the month and year of a treatment date or progression date is available, the day will be imputed to the 15th.

4.8.5. Concomitant Therapy

All medications will be coded to the generic preferred name according to the current World Health Organization drug dictionary. All concomitant medications will be summarized for the ITT population using the preferred name.

4.8.6. Poststudy Treatment Discontinuation Therapy

The numbers and percentages of participants receiving poststudy treatment discontinuation anticancer therapies will be provided by type of therapy (surgery, radiotherapy, or systemic therapy), and by drug class and/or name, overall, and by line of therapy.

4.8.7. Treatment Compliance

Treatment compliance of abemaciclib/placebo will be measured by pill counts and summarized. Compliance will be calculated as the ratio of total dose taken to the total assigned dose (minus any dose adjustments and doses omitted/withheld). The total assigned dose for a patient with no adjustments or omissions is 150 mg per dose \times 2 doses per day \times 28 days = 8400 mg. Fulvestrant is administered in the clinic. For analysis of fulvestrant exposure, see Section 4.7.1.

4.8.8. Follow-up Time

Follow-up time is defined as the time from the date of randomization until death from any cause or last date the patient is known to be alive and under follow-up. Median follow-up time will be estimated using Kaplan-Meier estimation of potential follow-up ("reverse Kaplan-Meier") (Schemper and Smith 1996). The inverse of the censoring rules for the OS will be used (ie, considering all censoring times for OS as event times [times when the patient is known to be still alive and under follow-up] and censoring patients who had OS events at the date of death).

4.8.9. Medical Resource Utilization

Frequency counts of hospitalizations, emergency room visits, radiation, surgery, transfusion, and analgesic use will be summarized descriptively by cycle and overall for each arm.

Duration of hospital stays and average number of emergency room visits will be reported by treatment arm.

4.8.10. Subgroup analyses

Subgroup analyses of PFS and OS will be performed for potential prognostic subgroup variables, including

- all baseline stratification factors
- measurable disease at baseline (yes versus no)
- age (<65 years versus \geq 65 years)
- race (Caucasian, Asian, and Other)
- progesterone receptor status (positive versus negative)
- baseline ECOG PS (0 versus 1)
- number of sites involved (1 versus 2 versus 3+)
- prior CDK4/6 inhibitor (abemaciclib versus palbociclib versus ribociclib), and

• prior CDK4/6 inhibitor setting (adjuvant versus locally advanced/metastatic)

If a level of a factor consists of fewer than 5% of randomized patients, analysis within that level will be omitted. Analyses will be done within subgroup and, separately, across subgroups with a test of interactions of subgroups with treatment performed. Estimated hazard ratios and CIs for the within subgroup analyses will be presented as a forest plot along with p-values for tests of interactions between subgroup variables and treatment. Other subgroup analyses may be performed as deemed appropriate. If any safety analyses identify important imbalances between arms, subgroup analyses of these endpoints may be performed.

4.8.11. Biomarker Analyses

The distributions of biomarkers with continuous measures, such as gene or protein expression, will be described. Summary statistics will include means, medians, corresponding standard errors, quartiles, and ranges. Biomarkers with discrete measures, such as genotype locus, will be summarized in frequency tables. Correlative analyses may be performed to investigate associations between biomarkers and clinical endpoints as deemed appropriate.

4.8.12. Important Protocol Deviations

Important protocol deviations that potentially compromise the data integrity and participants' safety will be summarized. These deviations will include deviations that can be identified programmatically and those which can only be identified by the clinical research associates during monitoring. Important protocol deviations are described in another document within the study Trial Master File.

4.9. Interim Analyses

4.9.1. Data Monitoring Committee

Interim analyses for safety and efficacy will be conducted under the guidance of an independent DMC. The DMC will consist of at least 3 members, including 2 clinicians and 1 statistician. The DMC will communicate any recommendations based on interim analysis to the Sponsor SMD. If necessary, the SMD may form an IRC to review and act upon the recommendations of the DMC. Details will be provided in a separate DMC charter.

4.9.2. Safety Interim Analyses

The DMC will monitor the overall safety of the study. The DMC members will review unblinded safety data at each interim analysis. If a significant safety signal is identified, the DMC may recommend a protocol amendment, termination of enrollment, and/or termination of study treatment. The recommendations of the DMC will be communicated to the SMD.

In the event that blinded safety monitoring by the study team uncovers an issue that needs to be addressed by unblinding at the treatment group level, members of the DMC can conduct additional analyses of the safety data. Additionally, unblinding of a limited number of the Sponsor representatives external to the study team may be required for evaluation of selected serious adverse events for determination of regulatory reporting.

There will be no prespecified rules for stopping the trial due to safety concerns.

The DMC will meet and review the overall data approximately every 6 months thereafter while patients remain in the on-study intervention periods. At the recommendation of the DMC, the frequency of safety interim analyses may be modified.

4.9.3. Efficacy/Futility Interim Analyses

The interim PFS analysis for efficacy will be conducted once approximately 176 PFS events in total (approximately 70% information fraction) have been observed with Type I error controlled via the sequential monitoring approach of DeMets and Lan (1994) with the O'Brien-Fleming type spending function. The critical p-value boundaries, cumulative Type I error rate, and cumulative power is provided in Table 6. At the interim analysis, the monitoring for futility will be conducted. Futility should be declared if the observed hazard ratio is ≥ 1.03 . Note the boundaries will be updated based on the number of events actually observed at each analysis.

If the futility boundary is met at the interim analysis, the DMC should inform the SMD and recommend that the study be stopped for futility. The SMD may convene an IRC to review the DMC's recommendation prior to making a decision based on the DMC recommendation. If the study is deemed to be futile, patients receiving active treatment may stop the blinded study drug depending on the data. Long-term follow-up of patients, including data collection on outcomes and sample collection, will proceed per protocol. If enrollment has not been completed at the time the study is deemed futile by the IRC, enrollment will be stopped. Planned study enrollment will continue during the conduct of the interim analysis.

The sponsor has no intent to stop the study based on interim analysis of efficacy, and all patients will continue follow-up for PFS until the primary PFS analysis and for OS until study close. If statistical significance is achieved for PFS at interim or final PFS analysis, an interim efficacy analysis of OS will also be conducted; the DMC will be instructed to recommend to the SMD that the results be released to the Sponsor. The SMD may convene an IRC to review the DMC's recommendation prior to Sponsor unblinding.

| Analysis | Number of Events | Information Fraction | HR Boundary for Futility | Critical one- sided P-value Boundary for Efficacy | Critical Hazard Ratio Boundary | Cumulative Type I Error Rate | Cumulative Power under Assumed HR of 0.7 |
|----------------|---------------------|-------------------------|--------------------------------|--|--------------------------------------|------------------------------------|---|
| Interim PFS | 176 | 70% | 1.03 | 0.007 | 0.69 | 0.007 | 0.472 |
| Final PFS | 251 | 100% | NA | 0.023 | 0.78 | 0.025 | 0.801 |

Abbreviations: HR = hazard ratio; PFS = progression-free survival; NA = not applicable.

5. Sample Size Determination

The study will randomize approximately 350 participants in 1:1 randomization ratio, with approximately 175 participants per treatment arm.

A 2-look group-sequential design of the primary endpoint of investigator-assessed PFS will be used to accommodate an event-driven plan for an interim PFS and final PFS analyses. The interim efficacy analysis will be performed after approximately 176 PFS events in total have occurred (ie, approximately 70% of the planned PFS events).

The final PFS analysis will be performed after approximately 251 PFS events in total have occurred (that is, an approximately 30% censoring rate). Assuming a hazard ratio of 0.70, this sample size yields approximately 80% statistical power to detect superiority for the abemaciclib plus fulvestrant arm versus the placebo plus fulvestrant arm.

This will be conducted with a one-sided log-rank test and a cumulative Type I error of 0.025.

6. Supporting Documentation

